## 7.4.2 Dose Adjustment and Discontinuation of Methotrexate

Methotrexate is contraindicated in LGLL patients with an estimated glomerular filtration rate (eGFR) <30 mL/min. For patients with an eGFR of 30 to 59 mL/min, a lower initial dosage is required; and a more gradual dose increase, close monitoring, and a lower maximum weekly dose should be considered, depending on the overall clinical conditions. Although low doses of methotrexate are not nephrotoxic, methotrexate is almost completely excreted through the kidney. Therefore, kidney function should be monitored. If renal insufficiency occurs, the methotrexate dose should be reduced or discontinued.

Guidelines from Cancer Care Ontario in Canada recommend a 25% reduction of dose at CrCl of 80 mL/min, 40% reduction at CrCl of 60 mL/min, 50% reduction at CrCl of 50 mL/min, and discontinuation at CrCl <50 mL/min. The guidelines also state that less conservative dose adjustments may be considered when using a low-dose regimen (<50 mg/m²). High-dose methotrexate could only be administered only when CrCl is >60 mL/min.

See Appendix 2 for the calculation method of CrCl.

## 7.4.3 Dose Adjustment and Discontinuation of Prednisone

The initial dose of prednisone is 0.5 mg/kg QOD, which should be adjusted according to the hematologic index. Actively monitor blood pressure and blood glucose, and observe adverse reactions of glucocorticoids. If there are adverse reactions of Grade 1 or 2, the dose can be reduced. If adverse reactions with ≥ Grade 3 occur, dose can be gradually reduced and eventually discontinued. If steroid-induced acute psychotic symptoms occur and antipsychotics are ineffective; or if corneal ulcers caused by the herpes virus occur, which can quickly lead to corneal perforation and may result in permanent blindness, discontinue the use of prednisone immediately or rapidly reduce the dosage significantly, instead of reducing it gradually.

#### 7.5 Other Treatment Considerations

During the patient's treatment, if unrelated illnesses or accidents occur, and there is a need to temporarily stop the treatment, it should be decided in consultation with the investigator.

# 8. Study Procedures

Only untreated or standard-of-care naive patients, patients with poor responses (failure to achieve PR) or relapse after receiving a non-methotrexate/thalidomide-based regimen, and patients who did not achieve PR within 4 weeks of methotrexate monotherapy can be enrolled in this study. Therefore, prior treatment and efficacy will also be evaluated before enrollment. The study consists of a screening period (Day –28 to Day 0), a treatment period, end of treatment, and a follow-up period.

# 8.1 Screening Period

All patients will undergo study eligibility screening, which will be completed within 4 weeks before the start of the study, including:

- Review of inclusion/exclusion criteria
- Physical examinations
- Vital signs measurements (body temperature, pulse, systolic and diastolic blood pressure, and respiratory rate)
- Height, weight, and body surface area
- ECOG performance status
- Disease-related signs and symptoms
- Assessment and recording of serious pre-treatment events
- Complete medical history (previous treatment and efficacy, enlargement of liver, spleen and lymph nodes; presence of other comorbidities)
- Hematology: Hemoglobin, ANC, WBC count, platelets
- Blood chemistry: Serum glucose, AST, ALT, total bilirubin, creatinine, Na, K, uric acid, total protein, and albumin
- Serum lactate dehydrogenase (LDH)
- Serum β2 microglobulin
- Serum immunoglobulin quantification
- Serological tests for HIV, hepatitis C virus (HCV), and HBV (including hepatitis B surface antigen [HBsAg], anti- hepatitis B surface antibody [HBsAb], and anti-hepatitis B core antibody [HBcAb])
- HBV-DNA and HCV RNA: HBV-DNA and HCV RNA will be used in patients with serologically positive HBV or HCV, respectively
- Coagulation function (8 items)
- Detection of peripheral blood lymphocyte subsets (B/T/NK; Treg; T-cell immune function; TH1/TH2)

- Peripheral blood flow cytometry
- Pregnancy test (if applicable)
- Urinalysis and stool
- Bone marrow aspiration and biopsy
- Bone marrow smear, immunohistochemistry, and flow immunophenotyping
- Flow cytometry detection of LGLs in patient's bone marrow fluid or peripheral blood; flow cytometry detection of killer immunoglobulin-like receptor; TCR rearrangement; TCRvβ flow cytometry, karyotyping; next generation sequencing
- Electrocardiograph (ECG)
- Computed tomography (CT) for assessment of measurable lesions (including neck, chest, abdomen, and pelvis)
- Assessment of cardiac function and ejection fraction by two-dimensional echocardiography; abdominal color Doppler ultrasound, etc.

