## 5 Study Population

Eligible patients will be screened within 28 days prior to the administration of the study drugs. Refer to Section 5.5, Screen Failures, for conditions that allow any screening procedure to be repeated.

The inclusion and exclusion criteria for patients enrolled in this study are summarized below. If there is any doubt about these criteria, the investigator must consult with the Sponsor representative and resolve all issues prior to study enrollment. No exemptions are allowed.

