# 5.5 Identification Codes, Enrollment, and Screening Log of Screening

## **Failed Patients**

Patients who meet the screening failure criteria may be rescreened. For abnormal screening values leading to exclusion during the screening period, it is allowed to retest (to reassess eligibility), and discuss with the Sponsor as appropriate. The last test result obtained prior to the first dose of the study drugs will be used to determine if a patient is eligible for the study. Measurements taken closest to the first dose of the study drugs (prior to the first dose) will be used as baseline values for safety assessments and treatment decisions.

The investigator will fill out the patient identification code and enrollment log to facilitate easy identification of each patient during and after completion of the study. The completeness of this document will be reviewed by the Sponsor's site contact. Patient identification codes and enrollment logs are confidential documents and will be kept by the investigator in the study documentation. To ensure the confidentiality of

patient's information, this document should not be copied. For all study-related reports and correspondences, patients will be identified by patient identification code and age on the initial ICF. If a patient is not enrolled in the study, the date when the patient is met and the age on the initial ICF will be used.

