#### Months 1 to 24 of TPM Treatment

- Physical examination and vital sign measurements
- ECOG performance status
- Assessment and recording of AEs to further assess whether the treatment can be continued
- Detection of LGLs in peripheral blood
- Hematology: Hemoglobin, ANC, WBC count, platelets.
- Blood chemistry: Serum glucose, AST, ALT, total bilirubin, creatinine, uric acid, etc.

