## At the End of Cycle 1 (Every 3 months as 1 cycle)

- Physical examination and basic vital sign measurements
- ECOG performance status
- Assessment and recording of AEs to further assess whether the treatment can be continued
- Hematology: Hemoglobin, ANC, WBC count, platelets
- Blood chemistry: Serum glucose, AST, ALT, total bilirubin, creatinine, uric acid, LDH, etc.
- Detection of LGLs in peripheral blood
- Detection of peripheral blood lymphocyte subsets (B/T/NK; Treg; T-cell immune function; TH1/TH2)
- Peripheral blood flow cytometry
- Peripheral blood TCRvβ flow cytometry
- Bone marrow smear, bone marrow biopsy, and immunohistochemistry
- Chromosome karyotype examination in bone marrow or peripheral blood
- ECG
- Evaluation of measurable lesions (including neck, chest, abdomen, and pelvis) by CT in patients with lymph node enlargement before admission
- Assessment of cardiac function and ejection fraction by two-dimensional echocardiography; abdominal color Doppler ultrasound, etc.
- Coagulation function

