## At the End of Cycles 2 to 8 (Every 3 months as 1 cycle)

- Physical examination and vital sign measurements
- ECOG performance status
- Assessment and recording of AEs to further assess whether the treatment can be continued
- Hematology: Hemoglobin, ANC, WBC count, platelets
- Blood chemistry: Serum glucose, AST, ALT, total bilirubin, creatinine, uric acid, LDH, etc.
- Detection of LGLs in peripheral blood
- Detection of peripheral blood lymphocyte subsets (B/T/NK; Treg; T-cell immune function; TH1/TH2)
- Peripheral blood flow cytometry
- Peripheral blood TCRvβ flow cytometry

- ECG
- Evaluation of measurable lesions (including neck, chest, abdomen, and pelvis) by CT in patients with lymph node enlargement before admission
- Assessment of cardiac function and ejection fraction by two-dimensional echocardiography; abdominal color Doppler ultrasound, etc.
- Coagulation function

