# 8.3 List of Tests and Key Time Points

Test	Screening/ Recurrence Progression	Post-Cycle 1	Every 3 Months Thereafter
Hematology	V	1	1
Blood type	1	,	Y
HIV/syphilis/hepatitis	V		
Complete test of viruses	V		
Lymphocyte subsets (at Blood	1	V	1
Research Institute)	,	'	'
All items of cytokines (at Blood	V	V	V
Research Institute is available)	,	,	,
Detection of peripheral blood	V	V	1
large granular lymphocytes	·	,	
TCRvβ flow cytometry	$\sqrt{}$	V	V
Immunoglobulin quantification	$\sqrt{}$		
Hepatorenal and cardiac function,	$\sqrt{}$	V	
blood glucose			
Electrolytes	V	V	V
Lactate dehydrogenase	V		
Blood β2-MG	$\sqrt{}$		
Coagulation (8 items)	$\sqrt{}$	V	V
Classification of bone marrow	V	When necessary	When necessary
smears		-	
Bone marrow biopsy (paraffin-		When necessary	When necessary
embedded)			
Flow immunophenotyping	$\sqrt{}$	When necessary	When necessary
Karyotype	$\sqrt{}$	When necessary	When necessary
TCR β、TCRγ、TCRδ		When necessary	When necessary
FISH	When necessary	When necessary	When necessary
Second-generation genetic testing	V		
Electrocardiograph	V	V	V
Cardiac color Doppler ultrasound	$\sqrt{}$	V	
(cardiac function)			
B-scan ultrasonography	√	V	V
(superficial lymph nodes)			
Cervical/chest/abdominal	$\sqrt{}$	When necessary	When necessary
computed tomography			
Test of infection foci	When necessary	When necessary	When necessary

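### Only one pregnancy test is listed, up to 28 days before the first thalidomide dose, and none at any routine visit during up to 2 years of treatment

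*Supplement*

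**What the plan says.** All references are to protocol version 2.0.

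- **Screening.** The Section 8.1 list includes "Pregnancy test (if applicable" as an item of its own, separate from blood chemistry. Section 5 sets the timing: "Eligible patients will be screened within 28 days prior to the administration of the study drugs". Section 8 describes a "screening period (Day –28 to Day 0".
- **Retesting.** Section 5.5 states: "For abnormal screening values leading to exclusion during the screening period, it is allowed to retest". It adds that the last result before the first dose decides eligibility.
- **On treatment.** Section 8.2 has three visit lists, headed "Months 1 to 24 of TPM Treatment", "At the End of Cycle 1 (Every 3 months as 1 cycle" and "At the End of Cycles 2 to 8 (Every 3 months as 1 cycle". None names a pregnancy test. The Section 8.3 table, "List of Tests and Key Time Points", has no pregnancy row as shown.
- **Progression.** Section 8.2.1 repeats the screening tests when the disease progresses.
- **Exposure.** Section 6.1 allows thalidomide for up to 2 years. Patients without clinical benefit leave after 6 months.
- **Risk and response.** Section 7.1 describes a very potent human teratogen that can do severe harm after one dose. Section 2.6.2 promises prompt withdrawal of women who become pregnant, and Section 5.3 lists pregnancy as a withdrawal criterion.
- **Other controls.** Section 5.2.2 excludes pregnant women and women of childbearing potential who are not using contraception. Section 6.3.3 prohibits hormonal contraceptives.

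**The concern.** There are two separate gaps.

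**Before the first dose.** If a single dose can cause severe harm, the test has to show that a woman is not pregnant when she takes that dose. A negative result that may be 28 days old does not show this, and nothing in the plan requires a newer one.

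**On treatment.** The plan commits to withdrawing women who become pregnant but schedules no test that would reveal a pregnancy. It would come to light through symptoms, an examination or an unscheduled test. Symptoms are a poor signal here. The protocol lists irregular menstruation as a prednisone effect (Section 7.3) and reports it in 12.5% of female patients in a Castleman disease study of a related thalidomide regimen (Section 2.5). Nausea is listed for both thalidomide and methotrexate (Sections 7.1 and 7.2).

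Section 2.6.2 names embryo-fetal toxicity and venous thromboembolism as the most severe thalidomide toxicities. Thromboembolism is met with an exclusion criterion, aspirin and coagulation tests at the end of every cycle. Embryo-fetal toxicity is met with an exclusion criterion and one screening test.

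**Working it through.** The plan gives no figure to reproduce. The check is a reading of every visit list in version 2.0, followed by simple counts.

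**1. Where a pregnancy test is listed**

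| Place | Pregnancy tests |
|---|---|
| 8.1 screening list | 1, if applicable |
| 8.2 list for Months 1 to 24 | 0 |
| 8.2 end of Cycle 1 | 0 |
| 8.2 end of Cycles 2 to 8 | 0 |
| 8.3 table, as shown | 0 in any column |
| 8.2.1 progression | 1, by reference to screening |

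The open-ended chemistry item in the 8.2 lists does not supply the test, because 8.1 keeps the pregnancy test apart from chemistry. The repeat at progression is not routine monitoring: it depends on an event, and progression is itself a withdrawal criterion (5.3, no. 2).

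**2. Age of the test at first dose**

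With screening allowed from Day -28 to Day 0, the test is 0 to 28 days old. The retest permission in 5.5 concerns abnormal values that led to exclusion, so a negative result on Day -28 prompts no repeat.

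**3. Cycle-end visits, at one per 3 months**

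- Full duration: 24 / 3 = 8 visits, 0 pregnancy tests.
- Leaving at 6 months: 6 / 3 = 2 visits, 0 tests.
- Leaving after the 3-month evaluation, which Section 4.3 allows: 3 / 3 = 1 visit, 0 tests.

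**4. Longest span from the screening test to the end of thalidomide with no scheduled test**

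Span = maximum test age + time on thalidomide, taking 24, 6 and 3 months as about 730, 183 and 91 days.

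- 24 months: 28 + 730 = 758 days.
- 6 months: 28 + 183 = 211 days.
- 3 months: 28 + 91 = 119 days.

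These are maxima. They assume a test on Day -28, no progression visit and no unscheduled test.

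**5. Gap if tests are added at existing draws**

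The longest gap between scheduled tests would be about 91 days with testing at cycle ends. It would be about 30 days if the Months 1 to 24 list is read as monthly visits, which its heading suggests but does not state.

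**6. Rough number of women concerned**

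Section 2.1 says about 10% of T-LGLL patients are under 40, with no gender difference. Section 4.5 plans at least 42 patients. Then 42 x 0.10 x 0.5 = 2.1, or about 2 women under 40. This assumes that age at onset stands in for age at enrolment, and it leaves out women over 40 who can still conceive. The documents give no pregnancy rate, so no number of pregnancies is estimated.

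**The case against.** The strongest reply is that the plan already prevents most of the risk and that few patients are concerned. Pregnant women and women not using contraception cannot enter, pregnancy leads to withdrawal, and Section 12.2 lets the investigator order a test needed for medical care. Perhaps 2 women under 40 would enrol. An on-treatment test cannot undo exposure that has already occurred.

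Much of this is true, and it puts the size of the problem in context. It does not close the gap. The contraception rule is an entry criterion, hormonal methods are barred, and a test is the check on contraceptive failure. Permission to test is not a requirement to test. On-treatment testing limits continued exposure even though it cannot reverse what has happened. Small numbers make the remedy cheaper but do not lessen the harm to the woman or child affected.

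Four narrower objections have some force:

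- The 8.3 table is weak evidence. It omits the pregnancy test even at screening, and also urinalysis and physical examination, so it is not a complete schedule. It serves only as corroboration.
- The early-withdrawal list in 8.4 also lacks the test, but that visit falls three months after the last treatment. Section 2.3 gives a half-life of 6 hours, with over 90% of absorbed drug excreted within 48 hours. Nothing here rests on that visit.
- Under 5.5 a later pre-dose test, if done, would decide eligibility. That is so, but none is required.
- Some patients will stop before 6 months. The 3-month case is therefore shown, and the day counts are upper limits.

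Labelling does not fill the gap either: Section 6.4 refers to local prescribing information only for dosage form, packaging and storage.

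**Conclusion.** The concern holds and should be fixed. Followed exactly, version 2.0 allows thalidomide to be started on a negative test up to 28 days old and continued for up to 2 years with no scheduled pregnancy test. The longest untested span is about 758 days at full duration, 211 days at 6 months and 119 days at 3 months.

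The seriousness rests on the protocol's own account of the harm and on the missing trigger for the withdrawal it promises. It does not rest on the day counts or on a large number of women at risk. The conclusion assumes that the Section 8 visit lists are the operative schedule and that no testing programme outside these documents applies; none is cited. The primary endpoint and its analysis are not affected.

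**What to change.** 1. **Section 8.1.** Keep the screening test and add a required negative test for women of childbearing potential immediately before the first thalidomide dose. State the window in the protocol.
2. **Section 8.2.** Add a pregnancy test to the Months 1 to 24 list and both end-of-cycle lists, for as long as thalidomide is taken. The sponsor and ethics committee should set the interval. Monthly testing limits continued exposure better than a gap of about 91 days.
3. **Section 8.3.** Add a matching row to the table.

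**Cost.** A short amendment and one inexpensive assay at visits where blood is already drawn. Tests per woman, in addition to screening:

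| Time on thalidomide | Cycle-end testing | Monthly testing |
|---|---|---|
| 24 months | 1 + 8 = 9 | 1 + 24 = 25 |
| 6 months | 1 + 2 = 3 | 1 + 6 = 7 |
| 3 months | 1 + 1 = 2 | 1 + 3 = 4 |

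For about 2 women, the most intensive option is 2 x 25 = 50 tests over the whole trial. Women over 40 who can still conceive would add to this.

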## Other test options:

Infection-related markers; fluorescence in situ immunohybridization (17p13); complete test of viruses, hemolysis-related tests (if relevant clinical manifestations are present): Coombs test and cold agglutinin test; rheumatoid factor, complement, ENA antibody spectrum, antinuclear antibody, antiplatelet antibody (when immune thrombocytopenia is suspected), antiphospholipid antibody (when combined with thrombus), serum ferritin plus serum iron test.

### 8.2 Treatment Period

Collect, record and report patient information and data in a timely manner to ensure that the data and information are timely, consistent, complete, reliable, and accurate. AEs, especially SAEs, should be treated in a timely and proper manner, timely tracked, followed up, recorded, and reported. Original records should be kept.

#### Months 1 to 24 of TPM Treatment

- Physical examination and vital sign measurements
- ECOG performance status
- Assessment and recording of AEs to further assess whether the treatment can be continued
- Detection of LGLs in peripheral blood
- Hematology: Hemoglobin, ANC, WBC count, platelets.
- Blood chemistry: Serum glucose, AST, ALT, total bilirubin, creatinine, uric acid, etc.

## At the End of Cycle 1 (Every 3 months as 1 cycle)

- Physical examination and basic vital sign measurements
- ECOG performance status
- Assessment and recording of AEs to further assess whether the treatment can be continued
- Hematology: Hemoglobin, ANC, WBC count, platelets
- Blood chemistry: Serum glucose, AST, ALT, total bilirubin, creatinine, uric acid, LDH, etc.
- Detection of LGLs in peripheral blood
- Detection of peripheral blood lymphocyte subsets (B/T/NK; Treg; T-cell immune function; TH1/TH2)
- Peripheral blood flow cytometry
- Peripheral blood TCRvβ flow cytometry
- Bone marrow smear, bone marrow biopsy, and immunohistochemistry
- Chromosome karyotype examination in bone marrow or peripheral blood
- ECG
- Evaluation of measurable lesions (including neck, chest, abdomen, and pelvis) by CT in patients with lymph node enlargement before admission
- Assessment of cardiac function and ejection fraction by two-dimensional echocardiography; abdominal color Doppler ultrasound, etc.
- Coagulation function

## At the End of Cycles 2 to 8 (Every 3 months as 1 cycle)

- Physical examination and vital sign measurements
- ECOG performance status
- Assessment and recording of AEs to further assess whether the treatment can be continued
- Hematology: Hemoglobin, ANC, WBC count, platelets
- Blood chemistry: Serum glucose, AST, ALT, total bilirubin, creatinine, uric acid, LDH, etc.
- Detection of LGLs in peripheral blood
- Detection of peripheral blood lymphocyte subsets (B/T/NK; Treg; T-cell immune function; TH1/TH2)
- Peripheral blood flow cytometry
- Peripheral blood TCRvβ flow cytometry

- ECG
- Evaluation of measurable lesions (including neck, chest, abdomen, and pelvis) by CT in patients with lymph node enlargement before admission
- Assessment of cardiac function and ejection fraction by two-dimensional echocardiography; abdominal color Doppler ultrasound, etc.
- Coagulation function

# 8.2.1 Disease Progression

The specific tests are the same as those in the screening period.

# 8.3 List of Tests and Key Time Points

Test	Screening/ Recurrence Progression	Post-Cycle 1	Every 3 Months Thereafter
Hematology	V	1	1
Blood type	1	,	Y
HIV/syphilis/hepatitis	V		
Complete test of viruses	V		
Lymphocyte subsets (at Blood	1	V	1
Research Institute)	,	'	'
All items of cytokines (at Blood	V	V	V
Research Institute is available)	,	,	,
Detection of peripheral blood	V	V	1
large granular lymphocytes	·	,	
TCRvβ flow cytometry	$\sqrt{}$	V	V
Immunoglobulin quantification	$\sqrt{}$		
Hepatorenal and cardiac function,	$\sqrt{}$	V	
blood glucose			
Electrolytes	V	V	V
Lactate dehydrogenase	V		
Blood β2-MG	$\sqrt{}$		
Coagulation (8 items)	$\sqrt{}$	V	V
Classification of bone marrow	V	When necessary	When necessary
smears		-	
Bone marrow biopsy (paraffin-		When necessary	When necessary
embedded)			
Flow immunophenotyping	$\sqrt{}$	When necessary	When necessary
Karyotype	$\sqrt{}$	When necessary	When necessary
TCR β、TCRγ、TCRδ		When necessary	When necessary
FISH	When necessary	When necessary	When necessary
Second-generation genetic testing	V		
Electrocardiograph	V	V	V
Cardiac color Doppler ultrasound	$\sqrt{}$	V	
(cardiac function)			
B-scan ultrasonography	√	V	V
(superficial lymph nodes)			
Cervical/chest/abdominal	$\sqrt{}$	When necessary	When necessary
computed tomography			
Test of infection foci	When necessary	When necessary	When necessary

# **8.4** Early Withdrawal (Discontinuation of Study Treatment)

### Three months after the Last Treatment:

- Physical examinations
- Vital signs measurements (body temperature, pulse, systolic and diastolic blood pressure, and respiratory rate)
- ECOG performance status
- Disease-related signs and symptoms
- Assessment and recording of AEs
- Hematology: Hemoglobin, ANC, WBC count, platelets
- Blood chemistry: Serum glucose, AST, ALT, total bilirubin, creatinine, Na, K, uric acid, total protein, and albumin
- Serum LDH
- Serum immunoglobulin quantification
- Urinalysis and stool
- Detection of LGLs in peripheral blood
- Detection of peripheral blood lymphocyte subsets (B/T/NK; Treg; T-cell immune function; TH1/TH2)
- Peripheral blood flow cytometry
- Peripheral blood TCRvβ flow cytometry
- Bone marrow smear, bone marrow biopsy, and immunohistochemistry
- Chromosome karyotype examination in bone marrow or peripheral blood
- ECG
- Evaluation of measurable lesions (including neck, chest, abdomen, and pelvis) by CT in patients with lymph node enlargement before admission
- Assessment of cardiac function and ejection fraction by two-dimensional echocardiography; abdominal color Doppler ultrasound, etc.
- Coagulation function

Following this assessment, patients will be followed up twice a year until the EOS, including survival, disease status, and long-term toxicity.

